## 1. PROTOCOL OVERVIEW

**Title:** Evaluation of Magseed as Localization Device for Biopsy Proven Metastatic Axillary Lymph Nodes in Women with Breast Cancer.

**Running Title:** Axillary Magseed Study.

**IRB Protocol Number:** 18-004803.

**Brief Study Description:** Pilot study to evaluate the safety and effectiveness of localizing biopsy proven metastatic axillary lymph nodes in women with breast cancer using Magseed markers as an alternative to the current practice of placing radioactive seed markers.

**Study Population:** Twenty patients with breast cancer will have a Magseed inserted into a biopsy proven metastatic axillary lymph node for pre-surgical localization.

## 2. STUDY BACKGROUND

Breast cancer patients with metastatic disease to the axilla historically have undergone a complete axillary lymph node dissection (ALND); however, this can result in significant morbidity. Alternatively, selective lymph node (SLN) surgery can be performed in patients who receive neoadjuvant chemotherapy (NAC) (1-3), since complete nodal response is seen in 41-74% of these patients (1, 4). The false negative rate of SLN surgery following NAC can be reduced by ensuring removal of a previously biopsy proven malignant lymph node (5). However, without preoperative localization, the biopsied lymph node is not obtained during the SLN surgery in around 23-25% of cases.

Currently at Mayo Clinic Rochester, breast cancer patients who are treated with NAC may have a biopsy clip placed in an axillary lymph node at the time or shortly after percutaneous sampling. Following 12-20+ weeks of NAC, preoperative localization of the sampled lymph node using a radioactive seed can be done up to 5 days prior to surgery. Localization of the sampled lymph node in patients with complete imaging response to NAC can be technically challenging if the biopsy clip is not sonographically visible, and has been shown to be successful in only 72% of cases (6). Here at Mayo, we place sonographically visually enhanced biopsy clips at the time of lymph node sampling; however, there is subset of patients where the clip is not readily identifiable particularly if there is an excellent response to the NAC. Mammographic localization can be achieved only if the biopsy clip can be included in the mammogram. If sonographic or mammographic localization of the biopsy clip is not possible, CT localization may be done, but this increases the cost of care, exposes the patient to a higher radiation dose, and potentially delays surgery.

An alternative to the radioactive seed is the Magseed (*Endomagetrics, Inc.*), a magnetic seed that uses an identical needle delivery system, that is FDA approved for long term placement into soft tissues prior to surgery. A recent study reported a 100% success rate of percutaneous preoperative localization of non-palpable breast lesions and surgical retrieval of the Magseed and intended breast target (7). However, given 3-4 cm of susceptibility artifact created by the Magseed on MRI, localization of the breast primary is recommended to be done only after all preoperative MR imaging is complete. The degree in which this artifact would interfere with the evaluation of the axilla is unknown as the axilla can also be evaluated with ultrasound to assess the response to NAC. MD Anderson currently is recruiting to an open label clinical trial evaluating placement of the Magseed into the axilla for preoperative localization after completion of NAC up to 30 days prior to surgery (NCT03038152). Recently, the Magseed was FDA cleared for soft tissues and long-term implementation, which means that the seed could be placed prior to initiation of NAC. Here at Mayo Clinic Rochester, the breast surgery group has a short-term trial approved to test the ease of use, intuitiveness, and accuracy of pre-surgical localization with the Magseed in the breast in our operating rooms, which would allow to also test the Magseed in the axilla.

Placement of a Magseed prior to NAC in the biopsy proven metastatic lymph node at or close to the time of the lymph node sampling would allow the lymph node to be identified at surgery following NAC without requiring the patient to undergo a second preoperative localization procedure. This would eliminate the need for the potentially time consuming and frustrating search for the axillary biopsy clip in patients with an excellent treatment response. Feasibility of localizing the sampled lymph node would be substantially higher prior to NAC, but it is unknown if this benefit outweighs the potential loss of information in assessing the axillary response to NAC on MRI due to the susceptibility artifact created by the Magseed in the axilla. It is expected that there would be negligible artifact to the ipsilateral breast tissue so the response to NAC for the breast primary could still be assessed accurately on MRI, but this may depend on both the location of the primary breast tumor(s) and the metastatic axillary lymph node, and requires further evaluation.

### 3. STUDY AIMS

**Aim 1:** Evaluate if Magseed is a viable alternative to radioactive seed as a localization method for biopsy proven metastatic breast carcinoma following neoadjuvant chemotherapy.

**Aim 2:** Determine the amount of artifact created by the Magseed in the axilla at MRI and identify imaging optimization to minimize the artifact produced by the magnetic clip.

**Aim 3:** Assess the success of retrieval of the Magseed and biopsy proven metastatic lymph node in the operating room compared to the current practice with the radioactive seed.

### 4. STUDY INCLUSION & EXCLUSION CRITERIA

**Study Population Target:** Twenty women with biopsy proven breast cancer and metastasis to an axillary lymph node

**Inclusion Criteria:**

1. Women 18 years or older
2. Neoadjuvant chemotherapy planned prior to surgical excision
3. Scheduled for target axillary lymph node dissection including the localized lymph node and sentinel lymph node

**Exclusion Criteria:**

1. Pregnant or nursing women
2. Allergy to lidocaine or gadolinium
3. Contraindication to MRI (i.e. pacemaker)
4. Axillary Infection
5. Prior axillary radiation
6. Known allergy to bone wax, beeswax or propolis

## 5. STUDY DESIGN

**Part 1:** Ten women with biopsy proven breast cancer and metastasis to an axillary lymph node will have a Magseed placed into the metastatic lymph node AFTER neoadjuvant chemotherapy (NAC) and just prior to surgery. These patients will have a non-contrast enhanced breast MRI development study to evaluate and identify ways to reduce the artifact in the axilla created by the Magseed. Efficacy of the localization with the Magseed will be available within a week of the placement.

**Part 2:** Ten additional women with biopsy proven breast cancer and metastasis to an axillary lymph node will have a Magseed placed into the metastatic lymph node BEFORE NAC. These patients will have routine contrast enhanced MRIs, mammograms, and ultrasounds before and after NAC to evaluate treatment response.

**Seed placement:** Once a patient has been identified eligible for the research study and has provided written informed consent they will have a Magseed placed into the biopsy proven lymph node. The Magseed delivery system is identical to our current practice using radioactive seeds. The seed is pre-loaded into the needle and is inserted into the lymph node following local anesthesia with 1% lidocaine. Once the seed is deployed, post procedure seed location is confirmed sonographically and mammographically with tomosynthesis.

**MRI:** Ten no-charge limited non-contrast breast MRIs for research development purposes are available for this study through the radiology department. Phase 1 participants will enroll in the study after their pre- and post-NAC imaging has already been performed per routine clinical practice. These participants will have a single non-contrast enhanced breast MRI using our

standard non-contrast sequences (axial ideal T1 and T2-weighted, axial STIR, and axial 3D vibrant using a dedicated breast coil, FOV 28 cm or to fit the patient size, and an image-thickness/image-increment of 5mm/1mm). A physicist will participate in the scanning of these patients to evaluate the extent of artifact in the axilla and adjacent breast tissue and optimize scanning parameters to reduce this artifact.

Phase 2 participants will enroll in the study prior to NAC and have routine contrast enhanced breast MRIs performed before and after NAC. Clinically indicated MRI scans will be charged to the patient's insurance company as this imaging is standard clinical practice. The MRI protocol will use our standard clinical sequences (axial ideal T1 and T2-weighted, axial STIR, and axial 3D vibrant using a dedicated breast coil). Once contrast is injected (gadobutrol 10mmol/10mL) 3D vibrant sequences will be obtained four times after contrast injection (FOV 28 cm or to fit the patient size, and an image-thickness/image-increment of 5mm/1mm).

**Mammogram:** Patients enrolled in the research study will have standard mammographic imaging before and after NAC, which will include both the breast and axilla as per routine clinical protocol.

**Ultrasound:** Patients enrolled in the research study will have standard sonographic imaging before and after NAC of the breast and axilla as per routine clinical protocol. Post-NAC ultrasound of the axilla will be a supplemental assessment to breast MRI as the Magseed artifact may obscure these findings.

**Seed Removal:** As per the current practice, patients will have targeted axillary lymph node dissection including both the localized lymph node and sentinel lymph node. Identifying the lymph node containing the Magseed will require the Sentimag handheld probe in the operating room. This device which functions similar to the gamma probe has been approved for an equipment trial starting in August of 2018. Once the lymph node has been excised a specimen radiograph will be obtained to verify removal.

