## 6. STUDY RISKS

**Seed Placement:** The Magseed is placed in an axillary lymph node using local anesthesia in an outpatient environment. There is a small risk of discomfort associated with the local anesthetic. There is a minor risk of infection and bleeding or bruising with the needle entry that is similar to a blood draw. Damage to adjacent structures including vessels or the lung are extremely rare with image guidance.

**MRI:** There is no radiation associated with MRI, but patients with metal devices in their body like pacemakers, cannot have an MRI and will not be able to participate in the study.

Patients with claustrophobia may feel trapped in the MRI scanner and may not tolerate the examination. If the patient feels too confined in the MRI scanner the technologist will stop the examination.

The MRI machine makes loud noises, which can damage hearing. Because of this known risk all patients are required to wear ear protection during the MRI scan that will minimize the discomfort and keep the noise levels at a safe level.

Gadolinium is FDA-approved and routinely used for breast MRI exams. Gadolinium can cause discomfort, warm tingling feeling in the body, metallic taste in the mouth, nausea, or headache in about 1 in 100 patients. These side effects usually last only for a very short time and completely resolve. Severe allergic reactions to gadolinium are extremely rare and occur in about 1 in 300,000 people. The needle placed in the patient's vein may cause minor pain, bruising, or infection at the injection site. Studies have shown that small amounts of gadolinium may remain in the body of patients who have received these injections. The effect of this, if anything, is unknown at this time.

Gadolinium may harm a fetus and therefore, pregnant women will not be allowed to enroll on this study. Women of reproductive age will undergo urine pregnancy testing.

Magseed placement will interfere with visualizing the axilla on MRI. The extent to which the artifact could interfere with visualizing the adjacent breast tissue is unknown. This is way phase 1 will consist of ten patients who have already had all their standard breast imaging. The one-time limited non-contrast MRI will allow us to optimize scanning parameters and decrease the artifact for phase 2 participants receiving their standard MRI after Magseed placement.

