## 10. DATA MANAGEMENT & STATISTICAL CONSIDERATIONS

**Data Management:** The principle investigator and co-investigators will supervise the data collection management.

**Outcome analysis:** The successful placement of the Magseed into the metastatic axillary lymph node will be evaluated and recorded by the radiologist performing the procedure. This information will be document into the electronic medical records as per normal clinical practice, in addition this information stored in the database.

The degree in which the artifact created by the Magseed in the axilla obscures the axillary or adjacent breast findings will be evaluated and recorded by the radiologist interpreting the MRI. Treatment response based on mammographic and sonographic evaluation of the axilla will be evaluated and recorded by the radiologist. The radiologist will determine if the supplemental imaging with mammography and sonography adequately replaces visualization of the axilla on MRI. Imaging results will be records in standard radiological reports as well as the database.

The successful retrieval of the Magseed into the metastatic axillary lymph node will be evaluated by the surgeon and radiologist. These results will be reported in both the patients operative report as well as the research database.

**Adverse events:** Adverse events occurring during the research study will be recorded into the electronic medical records and recorded into the research database.

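### Does the unstated order of Magseed placement and pre-NAC MRI in Part 2 undermine the Section 10 judgement that mammography and ultrasound can replace axillary MRI?

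*Combined protocol and SAP*

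**What the plan says.** Section 5 (Study Design) says that Part 2 women "will have a Magseed placed into the metastatic lymph node BEFORE NAC". The MRI paragraph of the same section says they "have routine contrast enhanced breast MRIs performed before and after NAC". Both events are timed against NAC and neither against the other.

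Three other places bear on the order without settling it:

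- Section 2 (Study Background) envisages placing the seed at about the time the node is sampled and does not mention MRI.
- The seed placement paragraph of Section 5 ties the seed to eligibility and consent.
- Section 6 (Study Risks, MRI) speaks of Part 2 women having their standard MRI once the seed is in, without saying whether that means the scan before NAC, the one after, or both.

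For Part 1 the order is explicit. Section 5 states "Phase 1 participants will enroll in the study after their pre- and post-NAC imaging has already been performed per routine clinical practice", and Section 6 repeats that "phase 1 will consist of ten patients who have already had all their standard breast imaging".

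On outcomes, Section 10 has the interpreting radiologist record how far the Magseed artifact obscures the axilla or adjacent breast, and record treatment response on mammography and ultrasound. It then says: "The radiologist will determine if the supplemental imaging with mammography and sonography adequately replaces visualization of the axilla on MRI". It names no reference MRI for that decision. Section 5 on ultrasound adds: "Post-NAC ultrasound of the axilla will be a supplemental assessment to breast MRI as the Magseed artifact may obscure these findings".

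**The concern.** Section 2 leaves open whether the gain from early placement is worth what it describes as a "potential loss of information in assessing the axillary response to NAC on MRI due to the susceptibility artifact created by the Magseed in the axilla". The Section 10 replacement judgement is the recorded outcome closest to that question. A reader would expect it to be set against an MRI on which the axilla can be seen, meaning one without the seed.

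The post-NAC MRI in Part 2 cannot be that scan, which leaves the pre-NAC MRI as the only candidate in that cohort, and its seed status is unstated. The order could even differ from one woman to the next. If so, the judgement might rest on no clear MRI in some women and on a clear baseline in others, and the number of scans able to show artifact would depend on an unrecorded choice. The protocol also makes no use of the seed-free routine imaging that Part 1 women bring with them.

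**Working it through.** The protocol gives no alpha, power or precision target and no figure on this point to reproduce. The check is a count of scans under each possible order, followed by a reading of what the Section 10 judgement covers.

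**Inputs.** Part 2 has ten women (Section 5), with one MRI before NAC and one after (assumption: every woman has both). The seed goes in before NAC (Section 5) and stays until surgery after NAC (Sections 2 and 5).

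**Count.** Let k be the number of Part 2 women whose seed is placed before the pre-NAC MRI, from 0 to 10.

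| Quantity | Formula | k = 0 | k = 5 | k = 10 |
|---|---|---|---|---|
| Seed-free pre-NAC MRIs | 10 − k | 10 | 5 | 0 |
| Seed-free post-NAC MRIs | 0 | 0 | 0 | 0 |
| Seed-in-place MRIs, both time points | 10 + k | 10 | 15 | 20 |

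The unknown order moves the first and third rows and leaves the second at zero.

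**Which row matters for the judgement.** In Section 10 the replacement sentence comes directly after the one on treatment response by mammography and ultrasound. It calls those modalities supplemental, and in Section 5 that word is attached to the ultrasound done after NAC. The judgement is therefore mainly a post-NAC one, and the relevant row is the second: 0 of 10 for every k. Stating the order would not change it. A seed-free scan before NAC precedes any response. It could show whether the modalities agree at baseline, but not whether mammography and ultrasound suffice for judging response.

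**Artifact outcome.** Section 10 records the degree to which the artifact created by the seed obscures findings. A scan without a seed has no such artifact. Splitting this outcome by seed status gives one stratum with all the information and one with none. The informative scans are the 10 + k with a seed in place. Seed placement and imaging results both go into the medical record and the research database (Section 10), so an analyst can identify those scans by comparing the two dates (assumption: the entries are dated). The radiologist reading the scan will in any case know whether a seed is there.

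**Using Part 1 as the comparator.** At most 10 pre-NAC + 10 post-NAC = 20 seed-free MRIs would be available, if each woman had MRI at both times. Suppose mammography and ultrasound agreed with MRI in all ten women at one time point. The exact (Clopper-Pearson) 95% lower limit is 0.025^(1/10) = 0.692, so the interval is 69% to 100%. With 9 of 10 it is 55% to 99.7%. These are illustrations only, because the protocol does not define agreement: it gives no rating, unit, threshold or blinding of readers. The analysis would also take MRI as the reference standard, and it would describe women without a seed at imaging, whereas the question concerns women with one.

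**The case for a change.** The best argument for a change is that it would be cheap and that the wording is truly open. The Section 6 remark about the standard MRI after placement can be read as meaning only the later scan or as including the earlier one. The order was written down for Part 1, and one sentence would do the same for Part 2. The protocol itself says the seed will interfere with the axilla on MRI, so seed status is no trivial detail. Section 10 names no comparator, and the Part 1 scans could supply one with no added imaging.

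Some of this stands. The order is not stated, a seed-free baseline MRI in Part 2 is not assured, and the replacement judgement has no named reference MRI. What does not stand is the step from there to a defect in the results. No two passages conflict, and no stated rule yields a wrong answer under either order. The lack of a clear post-NAC MRI comes from placing the seed before NAC. The protocol acknowledges this and plans axillary ultrasound for that reason.

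The Part 1 proposal costs more than it appears to. It is in effect a retrospective reader study. Section 5 says only that Part 1 women had routine imaging at both times, not that each had MRI, and the Part 2 text on billing speaks of scans that are clinically indicated: "Clinically indicated MRI scans will be charged to the patient's insurance company as this imaging is standard clinical practice". Whether the Part 1 consent covers research use of earlier images cannot be seen in the public text.

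**Conclusion.** No change to the plan is needed. The unstated order is missing operational detail that those reading and analysing the scans can fill from the images and the record. Its whole effect is on the number of seed-free baseline MRIs in Part 2 (0 to 10 of 10) and, correspondingly, of seed-in-place Part 2 MRIs (20 down to 10). It has no effect on the post-NAC replacement judgement, for which seed-free Part 2 MRIs are 0 of 10 under any order.

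Splitting the artifact outcome by seed status would add an empty stratum. A Part 1 agreement analysis would be a debatable addition to a descriptive pilot of twenty women, with a lower confidence limit of 69% even if agreement were perfect in ten.

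The conclusion assumes that all ten Part 2 women have both MRIs, that the replacement judgement is chiefly about response after NAC, as its place in Section 10 and the ultrasound paragraph of Section 5 indicate, and that placement and scan dates are recorded. Nothing here bears on which order of seed and MRI is clinically right.

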## 6. STUDY RISKS

**Seed Placement:** The Magseed is placed in an axillary lymph node using local anesthesia in an outpatient environment. There is a small risk of discomfort associated with the local anesthetic. There is a minor risk of infection and bleeding or bruising with the needle entry that is similar to a blood draw. Damage to adjacent structures including vessels or the lung are extremely rare with image guidance.

**MRI:** There is no radiation associated with MRI, but patients with metal devices in their body like pacemakers, cannot have an MRI and will not be able to participate in the study.

Patients with claustrophobia may feel trapped in the MRI scanner and may not tolerate the examination. If the patient feels too confined in the MRI scanner the technologist will stop the examination.

The MRI machine makes loud noises, which can damage hearing. Because of this known risk all patients are required to wear ear protection during the MRI scan that will minimize the discomfort and keep the noise levels at a safe level.

Gadolinium is FDA-approved and routinely used for breast MRI exams. Gadolinium can cause discomfort, warm tingling feeling in the body, metallic taste in the mouth, nausea, or headache in about 1 in 100 patients. These side effects usually last only for a very short time and completely resolve. Severe allergic reactions to gadolinium are extremely rare and occur in about 1 in 300,000 people. The needle placed in the patient's vein may cause minor pain, bruising, or infection at the injection site. Studies have shown that small amounts of gadolinium may remain in the body of patients who have received these injections. The effect of this, if anything, is unknown at this time.

Gadolinium may harm a fetus and therefore, pregnant women will not be allowed to enroll on this study. Women of reproductive age will undergo urine pregnancy testing.

Magseed placement will interfere with visualizing the axilla on MRI. The extent to which the artifact could interfere with visualizing the adjacent breast tissue is unknown. This is way phase 1 will consist of ten patients who have already had all their standard breast imaging. The one-time limited non-contrast MRI will allow us to optimize scanning parameters and decrease the artifact for phase 2 participants receiving their standard MRI after Magseed placement.

**Mammogram:** Inherent risks include added radiation dose. The MQSA (Mammography Quality Standards Act) recommended average glandular dose limit for screening mammography to 3mGy per view, which equals 12 mGy for a standard 4-view mammogram. There is no set limit for average glandular dose for diagnostic mammography. This is because the number of mammographic views for each patient varies based upon the images necessary to work up any particular finding. All diagnostic mammography will be within current clinical guidelines and well below levels that are known to cause long term side effects.

**Magseed:** The Magseed needle contains bone wax, which contains natural beeswax. There is a potential for a very minimal risk for an allergic reaction or a foreign body reaction (granuloma). To further minimize this risk, patients with known allergies to bone wax, beeswax or propolis will be excluded from the study.

